## **7.7 EXTENT OF EXPOSURE**

Descriptive statistics are planned for this section of the report based on the TS. The date and time of drug administration will be listed for each subject.

## **7.8 SAFETY ANALYSIS**

All safety analyses will be performed on the TS, separately for SRD and FE part.

If not stated otherwise, the safety results will be sorted by treatment group (SRD part) or by actual treatment (FE part).

The safety data for treated subjects who failed to complete the study (dropouts or withdrawals) will be reported as far as their data are available. All withdrawals will be documented and the reason for withdrawal recorded.

### **7.8.1 Adverse events**

AEs will be coded with the most recent version of MedDRA.

The analyses of AEs will be descriptive in nature and will be based on BI standards as presented in the corporate guideline: “Analysis and Presentation of Adverse Event Data from Clinical Trials” [001-MCG-156] ([9](#)).

The standard AE analyses will be based on the number of subjects with AEs (and not on the number of AEs).

For analysis multiple AE occurrence data on the CRF will be collapsed into an AE provided that all of the following applies:

- All AE attributes are identical (lower level term (LLT), intensity, action taken, therapy required, seriousness, reason for seriousness, relationship, outcome, AE of special interest)
- The occurrences were time-overlapping or time-adjacent (time-adjacency of two occurrences is given if the second occurrence started within one hour after end of the first occurrence)

For further details on summarization of AE data, please refer to [001-MCG-156] ([9](#)).

**Section 5.2.2.1 of the CTP: The following are considered as AESI in this trial:**

- *Hepatic injury, as defined by the following alterations of hepatic laboratory parameters:*
  - *an elevation of AST and/or ALT  $\geq 3$ -fold ULN combined with an elevation of total bilirubin  $\geq 2$ -fold ULN measured in the same blood sample, and/or*
  - *aminotransferase (ALT, and/or AST) elevations  $\geq 10$  fold ULN*

*These lab findings constitute a hepatic injury alert and the patients showing these lab abnormalities need to be followed up according to the 'DILI checklist' provided in the ISF. In case of clinical symptoms of hepatic injury (icterus, unexplained encephalopathy, unexplained coagulopathy, right upper quadrant abdominal pain, etc.) without lab results (ALT, AST, total bilirubin) available, the Investigator should make sure these parameters are analysed, if necessary in an unscheduled blood test. Should the results meet the criteria of hepatic injury alert, the procedures described in the DILI checklist should be followed.*

The analysis of adverse events will be based on the concept of treatment emergent adverse events.

**Section 5.2.2.2 of the CTP: The REP for BI 1358894, when measurable drug levels or PD effects are still likely to be present after the last administration, is not known for this first-in-human trial. Therefore, all AEs reported until the end of trial examination (last per protocol contact) will be considered on treatment [...].**

According to ICH E3 ([10](#)), AEs classified as 'other significant' needs to be reported and will include those non-serious and non-significant adverse events with  
(i) 'action taken = discontinuation' or 'action taken = reduced', or  
(ii) marked haematological and other lab abnormalities or lead to significant concomitant therapy as identified by the Clinical Monitor/Investigator at the RPM at the latest.

An overall summary of AEs (including AESIs) will be presented.

The frequency of subjects with AEs will be summarized by treatment, primary system organ class (SOC) and preferred term (PT). Separate tables will be provided for subjects with other significant AEs according to ICH E3 ([10](#)), for subjects with serious AEs, for subjects with drug-related AEs, for subjects with drug related serious adverse events and for subjects with AESIs.

The SOC and PTs will be sorted by frequency (within SOC). The MedDRA version number will be displayed as a footnote in the respective output.

In addition, frequencies of subjects with non-serious AEs that had an incidence of  $> 5\%$  for at least one treatment will be summarised by treatment, primary SOC and PT.

For disclosure of adverse events on EudraCT additional information not included in a standard AE analysis will be performed. The following three entries will be created:

- Adverse Events per arm for disclosure on EudraCT
- Non-serious Adverse Events for disclosure on EudraCT
- Serious Adverse Events for disclosure on EudraCT

### **7.8.2      Laboratory data**

The analyses of laboratory data will be descriptive in nature and will be based on BI standards [001-MCG-157] ([11](#)).

Laboratory data will be analysed qualitatively via comparison of laboratory data to their reference ranges. Values outside the reference range as well as values defined as possible clinically significant will be flagged in the data listings.

It is the investigator's responsibility to decide whether a lab value is clinically significant abnormal or not (at the RPM/DBLM at the latest).

### **7.8.3      Vital signs**

Descriptive statistics over time including change from baseline will be performed for vital signs (blood pressure and pulse rate), as well as respiratory rate (RR) and orthostatic tests (SRD part only).

### **7.8.4      ECG**

#### **Continuous safety ECG monitoring (by investigator) – (SRD part only)**

Clinically relevant abnormal findings will be reported as adverse events.  
No separate listing or analysis of continuous ECG monitoring will be prepared.

#### **12-lead ECG (SRD part + FE part)**

Abnormal findings will be reported as baseline conditions (at screening) or as AEs (during the trial) if judged clinically relevant by the investigator.

The descriptive evaluation of ECG data will be based on the TS, separately for the SRD part and the FE part.

#### **Listing of individual data**

For all quantitative endpoints, listings of individual data will be shown in Appendix 16.2. For QTcB and RR only listings will be provided. Occurrences of notable findings will be flagged.

Comments regarding the ECGs will be listed.

## 7.8.5 Others

### 7.8.5.1 Physical examination

Physical examination findings will be reported as relevant medical history/baseline condition (i.e., a condition already existent before intake of study drug) or as AE and will be summarised as such.

No separate listing or analysis of physical examination findings will be prepared.

### 7.8.5.2 Neurological examination

Neurological examination findings will be reported as relevant medical history/baseline condition (i.e., a condition already existent before intake of study drug) or as AE and will be summarised as such.

No separate listing or analysis of neurological examination findings will be prepared.

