4	29 to 33			End of trial (EOT) examination ⁴	x					x x	x x	

1. Subject must be informed and written informed consent obtained prior to starting any screening procedures. Screening procedures include physical examination, neurological examination, check of vital signs, ECG, safety laboratory (including drug screening, hepatitis serology and HIV antibodies), demographics (including determination of body height and weight, smoking status and alcohol history), relevant medical history, concomitant therapy and review of inclusion/exclusion criteria, Bond & Lader and Bowdle visual analogue scales and suicidality assessment (C-SSRS).

Proprietary confidential information © 2018 Boehringer Ingelheim International GmbH or one or more of its affiliated companies

2. The time is approximate; the respective procedure is to be performed and completed within 2 h prior to drug administration. Allocation to treatment may be performed at any time following enrolment but must be completed prior to (first) drug administration.
3. If several actions are indicated at the same time point, the intake of meals will be the last action.
4. End of trial examination includes physical examination, neurological examination, body weight, vital signs, ECG, safety laboratory, recording of AEs and concomitant therapies, Bond & Lader and Bowdle visual analogue scales and suicidality assessment (C-SSRS).
5. Only urine drug screening and alcohol breath test will be done at this time point.
6. AEs and concomitant therapies will be recorded throughout the trial, but will be specifically asked for at the time points indicated in the [Flow Chart](#) above.
7. Safety laboratory to be taken and to be medically evaluated within 3 days prior to administration of study drug; this safety laboratory can be omitted, if the screening examination is performed on Days -3, -2 or -1.

12. Suicidality assessment at screening, discharge from CPU and end of trial.
13. Confirmation of fitness includes physical examination, neurological examination, vital signs, ECG, recording of AEs and concomitant therapies. Evaluation of safety lab assessed on Day 2 and 5.

TABLE OF CONTENTS

TITLE PAGE	1
CLINICAL TRIAL PROTOCOL SYNOPSIS	2
FLOW CHART	5
TABLE OF CONTENTS	11
ABBREVIATIONS	15
1. INTRODUCTION.....	18
1.1 MEDICAL BACKGROUND	18
1.2 DRUG PROFILE	19
1.2.1 Nonclinical pharmacology.....	19
1.2.2 Safety pharmacology	19
1.2.3 Toxicology.....	20
1.2.3.1 Single dose toxicity.....	20
1.2.3.2 Repeat-dose toxicity studies	20

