5.2.5.6 Neurological examinations

As a general additional safety measure in the planned dose group 200mg fed a physical neurological examination will be performed at the time points specified in the respective [Flow Chart](#).

The neurological examination will include the following assessments:

- General level of arousal
- Orientation
- Eye movement
- Pupil size and pupil reactivity
- Reflexes
- Assessment of muscle strength
- Gait
- Romberg test
- Tremor
- Point-to-point movements
- Sensitivity

Documentation, Assessment, and Reporting

Results will be documented in source data at the clinical trial site and assessed for clinical relevance by an investigator, deputy investigator or sub-investigator. Clinically relevant findings of the neurological examination will be reported as Adverse Events (during the trial) or as baseline conditions (at screening). Case narratives may be written if necessary.

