6. INVESTIGATIONAL PLAN

6.1 VISIT SCHEDULE

Exact times of measurements outside the permitted time windows will be documented. The acceptable time windows for screening and end of trial examination are given in the [Flow Chart](#).

Study measurements and assessments scheduled to occur ‘before’ trial medication administration on Day 1 are to be performed and completed within a 2 h-period prior to the trial drug administration (including blank values for PK and biomarkers).

The acceptable deviation from the scheduled time for vital signs, orthostatic testing and ECG will be \pm 10 min and laboratory tests will be \pm 30 min for the first 4 h after trial drug administration and \pm 30 min thereafter.

If scheduled in the [Flow Chart](#) at the same time as a meal, blood sampling, vital signs and 12-lead ECG recordings have to be done first. Furthermore, if several measurements including venipuncture are scheduled for the same time, venipuncture should be the last of the measurements due to its inconvenience to the subject and possible influence on physiological parameters except for the orthostatic testing.

The acceptable deviation from the scheduled time for standardized neurological tests (conducted in Dose Group 200 mg fed) is \pm 45 min on day 1, and \pm 90 min from day 2 onwards.

For planned individual plasma concentration sampling times refer to the [Flow Chart](#). While these nominal times should be adhered to as closely as possible, the actual sampling times will be recorded and used for determination of pharmacokinetic parameter.

If a subject misses an appointment, it will be rescheduled if possible. The relevance of measurements outside the permitted time windows will be assessed no later than at the Blinded Report Planning Meeting.

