## 7. PLANNED ANALYSIS

The SRD and FE part will be evaluated separately.

The placebo group in the safety evaluation of the SRD part will consist of all placebo treated subjects, regardless of the dose group in which they were treated.

Safety analysis (refer to [Section 7.8](#)) will be performed by and will be presented in Sections 15.1 to 15.4 of the CTR and in Appendix 16.2 and 16.1.13.1.

Inferential statistical analyses of PK endpoints (refer to [Section 7.5.2](#)) will also be performed by and will be presented in Section 15.5 of the CTR and in Appendix 16.1.13.3.

Descriptive data analysis of PK parameters and concentrations will be performed by the department of Translational Medicine and Clinical Pharmacology at BI and will be presented in Section 15.6 of the CTR.

The format of the listings and tables will follow the standards defined in the BI corporate guideline “Reporting of Clinical Trials and Project Summaries” [001-MCG-159] ([6](#)) with the exception of those generated for PK-calculations.

In the SRD part, the individual values of all subjects will be listed, sorted by treatment group, subject number, and visit.

In the FE part, the individual values of all subjects will be listed, sorted by treatment sequence, subject number, visit and actual treatment (if appropriate).

The listings will be included in Appendix 16.2 of the CTR.

For end-of-text tables, the set of summary statistics for non-PK parameters is:

N	number non-missing observations
Mean	arithmetic mean
SD	standard deviation
Min	minimum
Median	median
Max	maximum

For analyte concentrations, the following descriptive statistics will additionally be calculated:

CV	arithmetic coefficient of variation
gMean	geometric mean
gCV	geometric coefficient of variation

For PK parameters, the following descriptive statistics will additionally be calculated:

CV	arithmetic coefficient of variation
gMean	geometric mean
gCV	geometric coefficient of variation
P10	10th percentile

Q1	1st quartile
Q3	3rd quartile
P90	90th percentile

The data format for descriptive statistics of concentrations will be identical with the data format of the respective concentrations. The descriptive statistics of PK parameters will be calculated using the individual values with the number of decimal places as provided by the evaluation program. Then the individual values as well as the descriptive statistics will be reported with three significant digits in the CTR.

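### AEs found by a neurological examination scheduled only in the 200 mg fed group are not identified as such, although 14 of the 16 pooled placebo subjects had no such examination

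*SAP*

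**What the plan says.** Protocol 5.2.5.6 introduces the examination for one group: "As a general additional safety measure in the planned dose group 200mg fed a physical neurological examination will be performed". It has 11 items, among them reflexes, pupils, Romberg test, tremor and gait. Protocol 6.1 repeats the restriction when it sets time windows for this group's tests.

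The footnotes to the 200 mg fed flow chart place it at screening, at discharge ("Confirmation of fitness includes physical examination, neurological examination, vital signs, ECG, recording of AEs and concomitant therapies") and at the end ("End of trial examination includes physical examination, neurological examination, body weight, vital signs, ECG, safety laboratory"). The corresponding footnotes for the 3 to 200 mg fasted groups list a physical examination at the same milestones, without a neurological one.

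Protocol 5.2.5.6 then says: "Clinically relevant findings of the neurological examination will be reported as Adverse Events (during the trial) or as baseline conditions (at screening". Results are kept as source data at the site. SAP 7.8.5.2 summarises such findings only as baseline conditions or AEs and adds: "No separate listing or analysis of neurological examination findings will be prepared".

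On the comparator, SAP 7 says: "The placebo group in the safety evaluation of the SRD part will consist of all placebo treated subjects", whatever the dose group. The primary endpoint (Protocol 5.2.1, SAP 5.1) is the number of subjects with drug-related AEs, compared descriptively with placebo.

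**The concern.** SAP 7.8.5.2 follows the physical-examination rule in SAP 7.8.5.1 almost exactly. That rule suits an examination that every group has. It suits less well one that was added for a single group at the highest planned exposure, because it joins a group-specific means of detection to a comparison across groups.

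A sign that appears only when reflexes, pupils or balance are formally tested can enter the AE tables from 200 mg fed. The same sign in a fasted subject, or in a placebo subject of a fasted group, has no scheduled test to reveal it.

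The descriptive AE tables are the whole of the primary analysis. A higher count of nervous-system AEs at the top exposure of a CNS-active compound would be read as a dose effect, and part of it could come from the extra examination. Protocol 3.2 defends comparison across groups by expecting small time effects. A change in how events are found is not a time effect, and neither document discusses it.

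**Working it through.** **Subjects with and without the examination**

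Inputs: 8 SRD groups of 8 subjects, 6 active and 2 placebo (Protocol 3.1 and 3.2). Placebo is spread equally over groups 1 to 8, and group 8 is 200 mg fed (Protocol 4.1.4).

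- SRD total: 8 x (6 + 2) = 64, which is the protocol's figure. Adding the 24 food-effect subjects gives its total of 88.
- Pooled placebo: 8 x 2 = 16. Without the examination: 16 - 2 = 14, or 87.5%.
- Fasted active subjects, all without it: 7 x 6 = 42.
- SRD subjects without it: 42 + 14 = 56 of 64.
- If a ninth group were added, up to the cap of 72: 18 placebo subjects, 16 of them without it.

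The like-for-like comparison is therefore 6 active against 2 placebo, inside 200 mg fed. The food-effect groups also lack the examination, but SAP 7 evaluates them separately.

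**Illustration of size**

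The documents give no rates, so two quantities are assumed:

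- q: the share of examined subjects in whom the examination adds an AE, the same on drug and placebo.
- b: the share of subjects with an AE from any other source, independent of q.

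Expected proportion with any AE:

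- 200 mg fed active: b + q(1 - b)
- pooled placebo: b + (2/16) q(1 - b)
- difference: (14/16) q(1 - b) = 0.875 q(1 - b)

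| q | difference, b = 0 (ceiling) | difference, b = 20% | chance of at least one such finding in 6 active, 1 - (1 - q)^6 |
|---|---|---|---|
| 5% | 4.4 points | 3.5 points | 26% |
| 10% | 8.8 points | 7.0 points | 47% |
| 20% | 17.5 points | 14.0 points | 74% |

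Over b = 10 to 30% and q = 5 to 20%, the difference runs from 3.1 points (0.875 x 0.05 x 0.70) to 15.8 points (0.875 x 0.20 x 0.90).

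These figures are for all AEs. The primary endpoint also needs the investigator to attribute the event to drug. If a share r of such findings is attributed, equally on drug and placebo, q is replaced by qr. With r = 50%, the ceiling falls to 2.2 to 8.8 points. One active subject whose only drug-related AE came from this source moves the group's rate by 1/6 = 16.7 points.

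**The case against.** The strongest reply is that the effect may be negligible.

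- To count, a finding must be judged clinically relevant, be new since a screening neurological examination, and be missed by everything else. It must arise in healthy men aged 18 to 45 with CNS disease excluded. Nothing in the documents supports 5 to 20%. This stands: the range shows how the arithmetic behaves and estimates nothing.
- A reader might infer that neurological events cannot be detected outside 200 mg fed. The documents do not support that. Fasted groups have physical examinations at discharge and end of trial, repeated AE questioning, and the Bond & Lader and Bowdle scales. Altered arousal, gait or tremor may be noticed without a structured test. The concern is confined to signs that need one.
- A reader might also infer that findings vanish from the report, or that nothing in it could help. That too goes too far. Clinically relevant findings stay in the AE tables. SAP 7.8.1 tabulates drug-related AEs by system organ class and preferred term, SAP 7 lists individual data, and narratives are possible. What is missing is the means of detection and any finding not judged clinically relevant.
- Safety is descriptive (Protocol 7.2), so no test is invalidated. That limits the weight of the point. It does not answer it, because a descriptive comparison still has to be read.
- 200 mg fed also differs in confinement (144 h against 48 h) and in AE follow-up (end of trial at Day 29 to 33 against Day 10 to 14). Identifying examination-detected AEs leaves those differences in place. Equally, aligning follow-up would leave this one.

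**Conclusion.** The point holds as a limited one about unequal detection. One group of 8 has a scheduled structured examination that feeds the AE count. All 42 fasted active subjects and 14 of 16 pooled placebo subjects do not, and no planned output identifies the AEs it detects. Signs that need the examination can inflate the 200 mg fed count relative to both comparators.

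The size is unknown. The all-AE excess is at most 4.4 to 17.5 points if q is 5 to 20%, and 3.5 to 14.0 points with a 20% background. Both rates are assumptions, as is equal yield on drug and placebo. For the drug-related endpoint the excess is smaller, to the extent that findings are not attributed to drug. It would be wrong to quote these figures as a demonstrated bias in the primary endpoint.

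The counts are those of the planned eight groups. Some footnotes to the 200 mg fed flow chart are not in the public text, so the number of post-dose examinations cannot be fixed. The visible footnotes give at least two, and the windows in Protocol 6.1 for day 1 and from day 2 onwards suggest more. The conclusion does not depend on that number.

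**What to change.** Amend SAP 7.8.5.2, for the 8 subjects of 200 mg fed only:

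1. Flag AEs first detected at the scheduled neurological examination, and list them by subject, treatment and time.
2. Keep every AE in the main tables. Add one supportive display of overall and drug-related AEs in 200 mg fed, with and without flagged AEs, beside that group's own 2 placebo subjects.
3. Footnote the AE tables to say that no other dose group had this examination.

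The cost is SAP wording, one listing, one display and a footnote. No procedure, dose or main analysis changes. There are three drawbacks. The detection source has to be taken from site source data by staff who know the treatment, which is itself open to bias. Two placebo subjects are a thin comparator, so the display can put a finding in context but not settle it. The differences in confinement and follow-up length remain. The footnote needs no new data and should be added even if the source of some AEs cannot be recovered.

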### 7.8.5.3 Visual Analogue Scale (VAS) - Bond & Lader and Bowdle

The VAS will be used at screening and at end of trial examination, as well as on predose at visit 3 (FE part only) and planned times -1:00 (dose groups 3mg to 50mg), -0:30 (dose groups 100mg, 200mg and 200mg fed), 2:00, 4:00, 8:00, 24:00, 34:00 and 48:00 (SRD part only).

The last VAS assessments before drug administration will be considered as baseline.

The results of both VAS will be listed and descriptive statistics over time including change from baseline will be performed.

#### Visual analogue scale – Bond and Lader

For Bond and Lader VAS, three factors will be calculated using the loadings (regression weights) from the factor analysis in (12), which are shown in Table [7.8.5.3:1](#) below. The individual scores on each scale will be multiplied by the scale's factor loading and totaled within the three factors. The summed scores will then be divided by the sum of loadings for each factor.

$$\text{Alertness} = F_1 = 1 / \sum w_{1i} * \sum (w_{1i} * VAS_i)$$

$$\text{Contentment} = F_2 = 1 / \sum w_{2i} * \sum (w_{2i} * VAS_i)$$

$$\text{Calmness} = F_3 = 1 / \sum w_{3i} * \sum (w_{3i} * VAS_i)$$

where

$VAS_i$  measured scale i; where  $i = 1, \dots, 16$

$w_{fi}$  factor loading for factor f and scale i; where  $f = 1, 2, 3$  and  $i = 1, \dots, 16$ ,

Since some scales for these loadings are reversed compared to the scales in the questionnaire the corresponding individual scores have to be reversed (100 – measured score value (mm)) before multiplication. Descriptive statistics of the three factors over time and for the difference from baseline will be provided. Furthermore, for the SRD part, the change from

baseline of the three factors will be presented graphically over time (arithmetic means + standard deviation).

Table 7.8.5.3: 1 Factor loadings for Bond and Lader VAS

Measured score value		Factor loadings to		
		Alertness	Contentment	Calmness
Alert / Drowsy	1. Alert	0.827	0.088	0.008
Calm / Excited	2. Calm	0.049	0.029	0.845
Strong / Feeble	3. Strong	0.618	0.142	0.328
Muzzy / Clear-headed *	4. Clear-headed	0.755	0.149	0.080
Well-coordinated / Clumsy	5. Well-coordinated	0.642	0.122	0.424
Lethargic / Energetic *	6. Energetic	0.776	0.174	-0.019
Contented / Discontented	7. Contented	0.233	0.677	0.278
Troubled / Tranquil *	8. Tranquil	0.133	0.697	0.429
Mentally slow / Quick-witted *	9. Quick-witted	0.635	0.340	-0.138
Tense / Relaxed *	10. Relaxed	0.031	0.445	0.677
Attentive / Dreamy	11. Attentive	0.792	0.179	0.098
Incompetent / Proficient *	12. Proficient	0.593	0.328	0.027
Happy / Sad	13. Happy	0.270	0.823	0.051
Antagonistic / Amicable *	14. Amicable	0.159	0.738	0.172
Interested / Bored	15. Interested	0.614	0.412	-0.006
Withdrawn / Gregarious *	16. Gregarious	0.343	0.594	-0.217

\* Measured score value will be reversed

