5.2.5.3 Visual Analogue Scale (VAS)

Possible psychedelic effects will be monitored and evaluated as safety measurement by analogue scales developed by Bond and Lader [[R98-0752](#)] and Bowdle along with PK sampling. From these measurements, following factors are derived - external and internal perception, alertness, mood and calmness.

The VAS assessments 2 hours before drug administration will be considered as baseline. At each measuring time point indicated in the [Flow Chart](#), the subjects will assess their subjective impression by themselves by means of a visual analogue scales. The subjects will be asked to mark an adequate position on a line between the two limits characteristics. The length of the line will be exactly 100 mm, and will ascertain a score number (values between

0 and 100) by measuring the distance in mm from the beginning of the line to the position marked by the subject. The score will be documented in the electronic case report form.

The original English version is shown in [Appendix 10.1](#).

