10. APPENDICES

10.1 VISUAL ANALOGUE SCALE (VAS)

Visual Analogue Scales (Bond & Lader) –English version

(As described in : Bond A, Lader M. The use of analogue scales in rating subjective feelings.
Br J Med Psychol 1974;47:211-18) [[R98-0752](#)]

Please rate the way you feel in terms of the dimensions given below.

Regard the line as representing the full range of each dimension.

Rate your feelings as they are at the moment.

Mark clearly and perpendicularly across each line.

1	Alert	_____	Drowsy
2	Calm	_____	Excited
3	Strong	_____	Feeble
4	Confused	_____	Clear-headed
5	Well-coordinated	_____	Clumsy
6	Lethargic	_____	Energetic
7	Contented	_____	Discontented
8	Troubled	_____	Tranquil
9	Mentally slow	_____	Quick-witted
10	Tense	_____	Relaxed
11	Attentive	_____	Dreamy
12	Incompetent	_____	Proficient
13	Happy	_____	Sad
14	Antagonistic	_____	Amicable
15	Interested	_____	Bored
16	Withdrawn	_____	Gregarious

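### The Bond & Lader scoring reverses the eight items that already point the right way, so Alertness, Contentment and Calmness rise when subjects get worse

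*SAP*

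**What the plan says.** Protocol 5.2.5.3 gives each item a value from 0 to 100, obtained by "measuring the distance in mm from the beginning of the line to the position" marked by the subject. Appendix 10.1 prints the 16 items as word pairs. Eight have the favourable word first (for example Alert to Drowsy, Calm to Excited) and eight have it last (for example Lethargic to Energetic, Tense to Relaxed).

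SAP 7.8.5.3 combines the items into three factors named Alertness, Contentment and Calmness. Each is a weighted mean using the loadings in Table 7.8.5.3:1. The reason given for reversal is: "Since some scales for these loadings are reversed compared to the scales in the questionnaire the corresponding individual scores have to be reversed". The operation is 100 minus the measured millimetres, applied before weighting. The items concerned carry an asterisk with the footnote "Measured score value will be reversed". They are items 4, 6, 8, 9, 10, 12, 14 and 16; item 4, for instance, is "Muzzy / Clear-headed". Item 7, "Contented / Discontented", has no asterisk. The loading column labels every item by its favourable word (Alert, Calm, Clear-headed, Contented and so on). The SAP summarises the factors and their change from baseline, and plots the change for the single-rising-dose part. Neither document says what a higher factor score means.

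**The concern.** The SAP's own reason for reversing is a mismatch between the loading label and the questionnaire. By that test item 1 should be reversed: its label is Alert, but its score rises toward Drowsy. Item 4 should not be: its label is Clear-headed, and its score already rises toward Clear-headed. The asterisks do the opposite, and the same holds for all 16 items.

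These factors are the subjective sedation and mood readouts of a CNS compound in its first human trial. Protocol 2.3.2.2 assumes that CNS effects in healthy subjects are limited to reduced anxiety. Under the written rule a subject who becomes calmer shows a fall in Calmness, and a sedated subject shows a rise in Alertness. With no direction stated, readers will take the labels at face value. The same report shows the Bowdle scales, where the drowsy and anxious items rise as symptoms worsen. A sedated subject could therefore appear both drowsier and more alert, purely because of scoring.

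**Working it through.** The SAP gives no worked score to reproduce, so the check applies its formula as written.

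**Inputs**
- x_i: millimetres from the beginning of the line (Protocol 5.2.5.3), taken as the left end of the form in Appendix 10.1.
- Reversal: 100 − x_i for the starred items (SAP 7.8.5.3).
- Loadings w_fi: SAP Table 7.8.5.3:1. They sum to 7.470 (Alertness), 5.937 (Contentment) and 3.037 (Calmness), all positive.
- Score: F_f = Σ(w_fi × item_i) / Σ w_fi.

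**Step 1: direction of each item**

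| Items | Pole at 100 mm as measured | SAP treatment | Pole at 100 when weighted |
|---|---|---|---|
| 1, 2, 3, 5, 7, 11, 13, 15 | Unfavourable (Drowsy, Excited, Feeble, Clumsy, Discontented, Dreamy, Sad, Bored) | Unchanged | Unfavourable |
| 4, 6, 8, 9, 10, 12, 14, 16 | Favourable (Clear-headed, Energetic, Tranquil, Quick-witted, Relaxed, Proficient, Amicable, Gregarious) | 100 − x | Unfavourable |

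The main loadings on each factor are positive, so each factor rises toward the unfavourable pole.

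**Step 2: extreme profiles (Alertness / Contentment / Calmness)**

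| Reversal applied | All marks favourable | All marks unfavourable |
|---|---|---|
| Starred eight (SAP) | 0 / 0 / 0 | 100 / 100 / 100 |
| Other eight | 100 / 100 / 100 | 0 / 0 / 0 |
| None | 45.85 / 58.36 / 33.29 | 54.15 / 41.64 / 66.71 |

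The last row shows that some reversal is needed.

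**Step 3: size of a shift under the SAP rule**
- 30 mm toward Drowsy on item 1: Alertness changes by 30 × 0.827 / 7.470 = +3.32.
- 30 mm toward Discontented on item 7: Contentment changes by 30 × 0.677 / 5.937 = +3.42.
- 30 mm toward Excited on item 2: Calmness changes by 30 × 0.845 / 3.037 = +8.35.
- 20 mm worsening on the nine main alertness items (1, 3, 4, 5, 6, 9, 11, 12, 15; loadings sum to 6.252): Alertness changes by 20 × 6.252 / 7.470 = +16.74. Contentment changes by +6.52 and Calmness by +5.28.

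Reversing the other eight items gives the same magnitudes with a minus sign.

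**Step 4: relation between the two scorings**

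For every item, the SAP value and the value under the other reversal are x and 100 − x in some order, so they sum to 100. Hence F_SAP + F_other = Σ(w × 100) / Σ w = 100 for any profile. The SAP score is an exact mirror image: standard deviations are unchanged and every change from baseline has the opposite sign.

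**The case against.** The strongest reply is that the starred set does the essential job. It puts all 16 items in one direction, so the factors are not corrupted. That stands: no information is lost, and any result can be recovered as 100 minus the score. The factor names could also be read as names of dimensions, since the SAP never says that higher means more alert. But the loading labels use the favourable words, and nothing in either document says that higher means worse.

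A second reply is that the cited factor analysis may itself score toward the unfavourable pole, in which case the SAP would be following its source. This cannot be checked from the documents. It does not rescue the labels, because flipping all 16 items together flips the factor with them and leaves the loadings valid in either orientation.

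Third, the sign depends on the start of the line being the left end. If distance were measured from the right, the SAP rule would give the favourable profile 100/100/100 and the names would fit. No text supports that reading. The protocol does append only the original English version of the form.

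Finally, the consequences are bounded. These scales are further safety criteria, summarised descriptively, and no stopping criterion in Protocol 3.3.4.2 uses them. The individual VAS results are listed, the Bowdle items have explicit poles, and clinically relevant sedation can be reported as an adverse event. This limits the gravity of the error but does not remove it.

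**Conclusion.** The concern holds. Followed exactly, the SAP produces Alertness, Contentment and Calmness scores that run opposite to their names: 0/0/0 for the most favourable profile, 100/100/100 for the least favourable, and +16.7 on Alertness for a 20 mm worsening across the nine main alertness items. Every change from baseline has the wrong sign for its label. The conclusion assumes that millimetres are counted from the left end of the printed line, which is the natural reading of the protocol. It does not depend on how the cited factor analysis was oriented. Because the error is a pure mirror image in a descriptive safety analysis, it should be corrected before the factors are reported, but it does not touch the primary endpoint.

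**What to change.** In SAP 7.8.5.3 and Table 7.8.5.3:1, move the asterisks to items 1, 2, 3, 5, 7, 11, 13 and 15 and remove them from the present eight. A higher score then means more alert, more content or calmer. If the sponsor prefers to keep the present reversal, for example to follow the cited source, rename the factors to match their direction. In either case, print the direction in the title or footnote of every Bond & Lader factor table and plot, and state in the SAP that millimetres are counted from the left end of the line. The cost is one programming line and a footnote, with no new data.
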